Management of GI adverse effects following kidney transplantation has been established as a consistent challenge for transplant centers. Reduction of MPA immunosuppression may lead to adverse outcomes such as rejection or graft failure, and use of AZA has been associated with higher rates of graft loss. Everolimus has been studied in kidney transplant recipients, and has been shown to lead to similar rates of rejection and graft function compared to MPA. Thus, we have proposed this single-arm study to assess improvement in GI adverse effects in renal transplant recipients. If EVR demonstrates a significant benefit with regard to GI adverse effects while maintaining appropriate rejection prophylaxis, it may offer transplant a new option for patients who are experiencing such adverse effects while on MPA therapy.

We will assess patients within the first year post-transplant for signs and symptoms of GI adverse effects, and following ruling out infectious causes, they will be consented and converted to EVR at an initial dose of 1 mg PO BID, which will then be titrated to target trough goals between 3 - 8 ng/mL. Prior to drug initiation, patients will complete the GSRS and GIQLI surveys to assess for intensity of symptoms and associated quality of life. Patients will remain on study therapy for at least 12 months and GSRS and GIQLI will be repeated at 30 days, 3 months, 6 months, and 12 months.

These timelines were chosen to allow enough time to demonstrate a significant change in GSRS scores following conversion to EVR. We have chosen not to include an active control due to the added cost and time that would be required to enroll and follow the additional numbers needed. We will compare data on graft rejection, graft function, graft survival, and patient survival to an historic cohort of patients who were converted to AZA for GI adverse effects. They will be compared on a 2:1 basis to a group of randomly selected patients previously converted to AZA.

Objectives

Primary objectives

To determine if a switch from MMF or EC-MPS to Zortress (everolimus) due to GI intolerance results in improvement of GI symptoms, as measured with the GSRS survey.

Secondary objectives

To determine whether it is safe to switch from MMF or EC-MPS to Zortress (everolimus) due to GI intolerance from MMF/EC-MPS within 12 months post-renal transplantation.

[figure not shown]
Study design

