- 2. Adult kidney transplant recipients at Washington University/Barnes-Jewish Hospital
- 3. Experiencing GI toxicity from MPA as determined by the treating physician within 12 months postrenal transplant
- 4. On standard immunosuppression with tacrolimus and prednisone

Exclusion criteria

1. Dual organ or kidney after another solid organ transplant

2. Presence of a preexisting significant GI condition that does not have a presumed causal relationship with MPA

3. Evidence of any GI disorder induced by an infection, underlying medical condition, or concomitant medication other than MPA

- 4. eGFR<35 ml/min at time of possible conversion
- 5. Proteinuria >1 gram/day at time of possible conversion
- 6. Profound bone marrow suppression at the time of possible conversion as defined as:
 - Hemoglobin <10 g/dL
 - WBC <3 K/cumm
 - Platelets <100 K/cumm

7. Wound healing issues at time of possible conversion (eg, wound dehiscence, wound infection, incisional hernia, lymphocele, seroma)

8. Elevated total cholesterol (>350 mg/dL) and/or triglycerides (>500 ng/dL) at time of possible conversion

9. Hypersensitivity to everolimus, sirolimus, or other rapamycin deriviatives

Treatment

Investigational and control drugs

Patients enrolled in the trial will receive everolimus tablets at a starting dose of 1 mg PO BID, which will be dispensed in 0.5 mg tablets in blister-packages of 60-each.

Treatment arms

This will be a single-arm study. All patients enrolled with be assigned to the everolimus arm. We will include an observational retrospective analysis of those on AZA-based immunosuppression for comparison of risk of acute rejection, chronic rejection, graft-loss, and death, but these patients have already been allocated treatment and completed follow-up.

Treatment assignment

This will be a single-arm study. All patients enrolled with be assigned to the everolimus arm.

Treatment blinding

This will be an open-label study. All participants including researchers, subjects, and analysts will be aware of treatment allocation.

Treating the patient

Patient numbering

Patients will be numbered sequentially from 1 through 30 based on the order they complete consent and enrol in the study

Dispensing the study drug

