Data collection will occur via the RedCap system. All local staff have received training on RedCap. Multiple forms will be created, including a baseline/screening form, and visit-specific forms. Only investigators will have access and the ability to download data.

Database management and quality control

The principal investigator will take responsibility for assessing quality data entry by overseeing all data entry into the RedCap system.

Data analysis (Any or all sections may be included based on type of study)

Statistical analysis and report writing will be performed when the last subject has completed 12 months on study.

Populations for analysis

Subjects completing three months of therapy and returning for study visit #2 will be included in the primary analysis. All subjects receiving at least one dose of everolimus will be included in all outcomes related to safety.

Patient demographics/other baseline characteristics

Demographic and background information for the population will be summarized using frequency distribution (for categorical variables) and descriptive statistics of mean, median, maximum, minimum and standard deviation (for continuous variables).

Treatments (study drug, rescue medication, other concomitant therapies, compliance)

The number of patients remaining on study medication at each study visit will be recorded. Additionally, mean tacrolimus and everolimus levels will be reported at each study visit.

Analysis of the primary objective(s)

Variable

The primary variable is the resultant score derived from the GSRS, which ranges from 0 - 45, compared at enrollment and at visit 2 (end of month 3).

Statistical hypothesis, model, and method of analysis

The null hypothesis: Conversion from MPA-based immunosuppression to EVR-based immunosuppression will result in similar GSRS scores at 3 months compared to baseline.

We will analyze changes in the GSRS using a paired T-test.

Handling of missing values/censoring/discontinuations

We will not include patients in the primary analysis and subsequent analyses of efficacy if they drop out of the study. We will analyze safety endpoints from a modified ITT approach, whereby patients receiving at least one dose of everolimus are considered on therapy until the end of their study period (12 months).

Supportive analyses

A per-protocol set will be analyzed as a secondary endpoint with regards to safety endpoints, including BPAR, graft loss, and death.

Analysis of secondary objectives

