Efficacy (secondary)

We will conduct analysis of GIQLI scores at visit 2, 3, 4, and 6 compared with baseline assessment, as well as inter-visit comparisons. Additionally, we will conduct subscore analyses of the GSRS and GIQLI at each of these timepoints. The pre-specified domains of the GSRS to be analyzed will be the abdominal pain, diarrhea and reflux scores. The GIQLI subscores will be analyzed for all domains.

Safety

Safety variables to be assessed include BPAR, graft loss, death, graft function at each study visit, discontinuation from study, discontinuation from treatment, infection, SAE, notable events, laboratory tests, and vital signs. All safety analyses will be done on the safety set. Selected variables will be analyzed using all available data including data assessed.

Health-related Quality of Life

As above.

Sample size calculation

The sample size was calculated based on the myTIME study. Sample size calculation showed that a minimum sample size of 25 patients will be required to provided 80% power to detect a change from baseline of 12 points in the total GSRS score (15-105 scale) considering a 0.05 significance level and a standard deviation of 18 and allowing for a 20% dropout. A paired t test will be utilized to compare the overall GSRS score, the GSRS subscale scores, and the GIQLI from baseline.

- Assuming a 5% 1-year rate of acute rejection, we plan to evaluate 60 historical control patients to compare differences in the secondary endpoints of acute rejection, graft survival, patient survival, and infections. The historical control group will be randomly selected from a consecutive list of patients who received a renal transplant during the same study period and were maintained on MMF 500mg-1gram BID or EC-MPS 360-720mg BID, tacrolimus, and prednisone and met stated inclusion and exclusion criteria as listed below. 30 conversion patients will be enrolled and compared 1:2 with historical controls.
- Statistical analysis for the historical control comparison will utilize the Chi-squared test for events, ANOVA for renal function outcome differences and other continuous variables, and Kaplan-Meier estimates for patient and graft survival

Ethical considerations

Regulatory and ethical compliance

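### As worded, the MPA control rule can select historical controls on staying on their regimen, while everolimus patients count from the first dose, which could bias the secondary safety comparison against everolimus

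*Combined protocol and SAP*

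**What the plan says.** **Everolimus side.** Populations for analysis (10.1) states: "All subjects receiving at least one dose of everolimus will be included in all outcomes related to safety". Handling of missing values/censoring/discontinuations (10.4.3) calls this a modified ITT approach, under which "patients receiving at least one dose of everolimus are considered on therapy until the end of their study period (12 months"). Supportive analyses (10.4.4) adds: "A per-protocol set will be analyzed as a secondary endpoint with regards to safety endpoints, including BPAR, graft loss, and death".

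**Control side, sample size section (10.6).** Sixty controls are sampled at random from a consecutive list of transplant recipients who "were maintained on MMF 500mg-1gram BID or EC-MPS 360-720mg BID, tacrolimus, and prednisone and met stated inclusion and exclusion criteria". They are compared with 30 conversion patients on acute rejection, graft survival, patient survival and infections. The methods are a chi-squared test for events and Kaplan-Meier estimates for patient and graft survival.

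**Control side, elsewhere.** The body's Purpose and rationale describes a different group: "They will be compared on a 2:1 basis to a group of randomly selected patients previously converted to AZA". Treatment arms also describes azathioprine patients and notes that "these patients have already been allocated treatment and completed follow-up".

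No section gives the controls a time zero, says how long *maintained* must last, or says how a control who stopped, switched, lost the graft or died is counted.

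**The concern.** In a cohort comparison, membership should be fixed by what is known when follow-up starts. The everolimus rule does this: one dose puts a patient in, and nothing later takes the patient out. The control rule in 10.6 may not, because whether a patient was maintained on three drugs within an MPA dose range can be judged only by looking forward from the starting point.

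Rejection, infection and intolerance are reasons to change a regimen. A chart reviewer applying 10.6 could therefore leave out controls whose regimen changed after such events, while the corresponding everolimus patients remain and count as events. The control event rate would be too low and everolimus would look less safe than it is. Random sampling from a list already filtered in this way does not remove the problem.

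At stake is the comparison that supports the secondary objective, whether the switch is safe. Few events are expected, so one or two missing control events would change the picture.

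**Working it through.** **1. The plan's own figures.** The 25 patients in 10.6 come from a paired t-test with change 12, SD 18, 80% power and level 0.05 (taken as two-sided). The standardised effect is 12/18 = 0.667. The noncentral t gives n = 20 (power 80.7%; n = 19 gives 78.5%), and 20/0.8 = 25. That reproduces exactly, so no arithmetic error is involved. The 60 controls are 2 × 30; no power or detectable difference is stated for them.

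**2. Does *maintained* act as a filter?** The synopsis says that standard practice at this centre is to start MMF or EC-MPS, tacrolimus and prednisone immediately after transplant. If *maintained* meant only *started on*, it would exclude few patients from a consecutive list at this centre. The same text says that MPA reductions, interruptions and discontinuations are common and that patients may be switched to azathioprine. With its dose range, the phrase therefore most naturally selects patients who stayed on the regimen. The eligibility criteria do not supply a start date either: several exclusions are assessed at the time of possible conversion, but a patient who stayed on MPA has no conversion date.

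**3. Expected events.** At the plan's 5% one-year rejection rate: 0.05 × 60 = 3.0 in controls and 0.05 × 30 = 1.5 on everolimus.

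**4. Size of a possible bias.** Let p = 0.05 be the true rate in both groups, k the share of rejecting controls removed, and m the share of event-free controls removed. The documents give neither k nor m; both are assumptions.

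- Observed control rate = p(1−k) / [p(1−k) + (1−p)(1−m)]
- Apparent risk ratio = p / observed control rate = p + (1−p)(1−m)/(1−k)

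| k | m | Control rate | Apparent ratio | Chance of a significant chi-squared result |
|---|---|---|---|---|
| 0 | 0 | 5.0% | 1.0 | 3.6% |
| 0.25 | 0 | 0.0375/0.9875 = 3.8% | 1.32 | 6.3% |
| 0.5 | 0 | 0.025/0.975 = 2.6% | 1.95 | 11.9% |
| 0.75 | 0 | 0.0125/0.9625 = 1.3% | 3.85 | 22.8% |
| 0.5 | 0.25 | 0.025/0.7375 = 3.4% | 0.05 + 0.95 × 0.75/0.5 = 1.475 | not computed |
| any k below 1 | = k | 5.0% | 1.0 | 3.6% |

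The last column is an exact binomial enumeration of the uncorrected chi-squared test, 60 against 30, with no true difference. The rows with m = 0 and k above 0 are the extreme for each k. The formula also shows that the bias runs against everolimus only when k exceeds m, that is, when controls with events are more likely to be dropped than those without.

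**The case against.** **The word may only name a regimen.** The protocol speaks of triple maintenance immunosuppression, and no section says that controls who stop or switch are left out. The dose range is two-fold, so halving from its top still qualifies. This stands in part: exclusion of failures is a reading, not a stated rule. But it is the reading under which the phrase does any work at this centre, and nothing in the text rules it out.

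**The azathioprine group is free of it.** A reader might infer that the flaw exists whichever control drug is chosen. The documents do not support that. Purpose and rationale selects on prior conversion to azathioprine, which is a starting event, with no requirement to stay on it.

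**Completed follow-up is not an entry condition.** A reader might take that remark in Treatment arms as a second filter. It is ambiguous, but it reads as a description of a retrospective group. It belongs to the azathioprine patients and is never combined with the *maintained* wording. A patient who rejected, lost the graft or died can have a completed record, and the planned Kaplan-Meier estimates imply that deaths and graft losses are to be counted.

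**The background rates do not give the size.** The synopsis contrasts 30.2% rejection after GI complications with an MMF change against 19.4% without GI complications (ratio 1.56). That does not isolate a regimen change in comparable patients, and it says nothing about the share of rejecting patients whose regimen was then changed. It supports direction at most.

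**The comparison is secondary and weak.** Against 5% in 60 controls, rejection on everolimus would have to reach about 26.5% for 80% power, and a bias against everolimus would not create a false claim of safety. Both are true and limit the consequences. Neither makes the comparison valid, and the per-protocol set is only supportive.

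**Conclusion.** The point holds for the MPA control group in 10.6. Read as staying on the regimen, the selection rule conditions control entry on later information, while the everolimus rule does not. No index date or all-patients follow-up rule for controls corrects this. The likely direction is against everolimus, provided that controls with events are the more likely to be dropped.

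The size cannot be determined from the documents. At 5% true rejection in both groups, the apparent ratio runs from 1.0 (equal losses) through about 1.47 (k = 0.5, m = 0.25) to 1.3, 1.95 or 3.85 (k = 0.25, 0.5 or 0.75 with m = 0). All rest on assumed shares.

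A reader might go further and conclude that early failures are removed by rule; the text shows only that they could be. The effect is confined to the secondary comparison with historical controls. The primary GSRS analysis compares patients with their own baseline and is untouched.

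**What to change.** 1. Reconcile Purpose and rationale, Treatment arms and 10.6 so that they name one control group.
2. Select controls only on facts known at a defined index date. For MPA controls, replace the *maintained* wording with a requirement to be receiving the regimen and to be eligible on that date, and say how the date is set (for example, a matched time after transplant). For azathioprine controls, use the date of conversion.
3. State that completed follow-up is not a condition of entry.
4. Follow every sampled control for 12 months from the index date whatever happens to the drug, censoring incomplete follow-up. This mirrors the modified ITT rule for everolimus.
5. Apply any on-regimen restriction only in the per-protocol analysis, and to both groups.

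The cost is a change of wording and a wider chart query at the same centre, with no extra trial patients. Some controls will have incomplete follow-up and be censored. The change should be made before controls are drawn, because their outcomes are already in the charts and analysis cannot reliably undo a filtered selection.

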Study drug discontinuation	Point/time when patient permanently stops taking study drug for any reason; may or may not also be the point/time of premature patient withdrawal
Variable	Information used in the data analysis; derived directly or indirectly from data collected using specified assessments at specified timepoints

Protocol synopsis

Title of study: Conversion from MPA to Zortress (everolimus) for GI toxicity post-renal transplantation

This study is a prospective, single-center study to evaluate the effectiveness of conversion from MMF or EC-MPS to EVR during the first year post-renal transplant in patients who experience gastrointestinal adverse effects. The primary outcome will be change in GSRS from baseline (time of conversion) to 30 days post-conversion.

In total, 25 patients will be enrolled and converted from MPA to EVR, at an initial dose of 1 mg PO BID with target everolimus troughs between 3 - 8 ng/mL. Patients who are less than one year from date of transplant with identified GI symptoms who are on immunosuppression with tacrolimus, MPA, and prednisone will be enrolled and followed for 1 year. These patients will be compared to an historical cohort of patients receiving azathioprine for safety outcomes (including rejection and graft/patient survival).

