This study will be conducted over a 2-year period, during which patients will be enrolled through the first year, and follow-up of a minimum of 1 year will be collected on each patient. Interim analyses will be conducted at 6-months or upon enrollment of 15 patients (whichever is earliest). The interim analyses will assess the rate of study drug discontinuation due to non-efficacy (as determined by nephrologist). If more than 5 patients (33%) have discontinued drug due to non-efficacy, the study will be terminated. Additionally, any other problems or safety signals will be addressed by the research team at this time.

Subjects meeting criteria will be asked to sign an informed consent, and upon execution of informed consent this will be considered study day 1. They will examined on study day 1 including a medical history, medication history, vital signs, height, weight, and BMI. Subjects will complete GSRS and GIQLI surveys, report adverse effects, and complete laboratory tests, including tacrolimus levels. Subjects will have 5 additional visits during the study period, which will include a medication history, vital signs, height/weight/BMI, adverse effect recording, GSRS and GIQLI (excepting visit 5), laboratory work including tacrolimus and everolimus levels, and reporting of infectious symptoms. These visits will occur at the end of months 1, 3, 6, 9, and 12.

Figure Error! No text of specified style in document.-1 St

Study design

Population

We intend to include patients who have received kidney transplant at the Washington University/Barnes-Jewish Hospital transplant program in the year prior to enrollment who are exhibiting signs of non-infectious GI toxicity determined by the treating physician to be secondary to MPA. In total, 30 candidates will be enrolled and treated with conversion from MPA to EVR. We anticipate a dropout rate of 20%, and expect that 24 patients will complete a full year of study drug. Severity of GI adverse effects will be assessed using the GSRS and GIQLI scales, but no specific severity threshold will be used to enroll patients. The study will be conducted largely on outpatients, but patients may be initially enrolled during inpatient stays.

Inclusion criteria

Patients eligible for inclusion in this study have to fulfill all of the following criteria:

- 1. Patients must give written informed consent before any assessment is performed.

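### For rejection and infection, the safety question is to be answered by a chi-squared test of no difference in 30 versus 60 patients, whose non-significance cannot support safety or similarity

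*Combined protocol and SAP*

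**What the plan says.** The only secondary objective, in the synopsis and under Objectives, is a safety question: "To determine whether it is safe to switch from MMF or EC-MPS to Zortress (everolimus"). Purpose and rationale looks for a GI benefit "while maintaining appropriate rejection prophylaxis", and Background hopes that rejection will be about as frequent as with azathioprine.

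The comparison that bears on this is under Sample size calculation: "Assuming a 5% 1-year rate of acute rejection, we plan to evaluate 60 historical control patients to compare differences in the secondary endpoints". These endpoints are acute rejection, graft survival, patient survival and infections. The same paragraph adds: "30 conversion patients will be enrolled and compared 1:2 with historical controls".

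The method follows: "Statistical analysis for the historical control comparison will utilize the Chi-squared test for events". The rest of that sentence assigns ANOVA to renal function and other continuous variables, and Kaplan-Meier estimates to patient and graft survival. The Safety section lists many variables but names no method. Supportive analyses repeats rejection, graft loss and death in a per-protocol set, again without a method.

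For these events the plan gives no confidence interval, detectable difference, power, margin or exact test. It does not say whether the chi-squared test is continuity-corrected, and it has no rule for what result would bear on safety.

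**The concern.** A test of no difference can show that two rates differ. When it fails to do so, it shows similarity only if the study was large enough that an important excess would probably have been detected. Here the stated question is whether the switch is safe, the expected number of rejections is a handful, and the planned output for rejection and infection is a p-value. The likeliest result is a non-significant one, and it would carry almost no information about whether rejection had doubled or tripled.

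There is a second, smaller difficulty. With expected counts this low the chi-squared approximation is poor, and the usual versions of the test can disagree across the 0.05 line. The plan does not say which version applies.

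At stake is the wording of the safety conclusion. Nothing in the plan obliges the report to show how large an excess of rejection remains compatible with the data.

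**Working it through.** **Inputs.** From Sample size calculation: 5% one-year rejection, 30 converted patients, 60 controls, chi-squared test. From Populations for analysis: everyone with at least one dose enters the safety analyses, so the 30 is not reduced for dropout. Assumptions of mine: two-sided 0.05 (the plan gives a significance level only for the GSRS), and the 5% taken as the control rate. No infection rate is given, so the arithmetic is for rejection.

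**The plan's own figures.** The only powered figure is the 25 for the GSRS, and it reproduces. A paired t-test with 20 evaluable patients, a 12-point change and SD 18 has 80.7% power, and 20/(1 − 0.20) = 25. The 60 controls are 2 × 30, with no power statement to reproduce.

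**Expected events.** 30 × 0.05 = 1.5 and 60 × 0.05 = 3.0.

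**Chance of flagging an excess.** Sum over all tables: power = Σₐ Σ_b Bin(a; 30, p_E) × Bin(b; 60, 0.05), taken over tables with a/30 > b/60 and p < 0.05.

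| True rate on everolimus | Uncorrected | Yates | Fisher |
|---|---|---|---|
| 10% (2-fold) | 15.3% | 6.6% | 12.9% |
| 15% (3-fold) | 36.2% | 22.2% | 31.6% |
| 20% (4-fold) | 59.6% | 44.2% | 53.2% |
| 25% (5-fold) | 78.4% | 66.0% | 72.5% |

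So a doubling is missed 85% of the time (93% with Yates) and a tripling 64% (78%). Power passes 50% at a true rate of 17.9% for the uncorrected test (17.9/5 = 3.6-fold) and 21.3% with Yates (4.3-fold).

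**A result close to expectation: 2/30 against 3/60.** χ² = 90 × (2×57 − 28×3)² / (30 × 60 × 5 × 85) = 81,000/765,000 = 0.106, p = 0.74. The Wilson limits are 1.8% to 21.3% for 2/30 and 1.7% to 13.7% for 3/60, and the difference is 6.7 − 5.0 = 1.7 points. Newcombe limits:
- lower: 1.7 − √[(6.7 − 1.8)² + (13.7 − 5.0)²] = −8 points
- upper: 1.7 + √[(21.3 − 6.7)² + (5.0 − 1.7)²] = +17 points

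**A threefold observed excess: 5/30 against 3/60** (16.7% against 5%). χ² = 90 × (5×57 − 25×3)² / (30 × 60 × 8 × 82) = 3.36, p = 0.067. The Newcombe interval is −1 to +29 points.

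**Dependence on the version of the test: 2/30 against 0/60.**
- Uncorrected: χ² = 90 × 120² / (30 × 60 × 2 × 88) = 4.09, p = 0.043.
- Yates: χ² = 90 × (120 − 45)² / 316,800 = 1.60, p = 0.21.
- Fisher: (30×29/2)/(90×89/2) = 435/4,005, p = 0.11.

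**Sensitivity.** The synopsis has "In total, 25 patients will be enrolled and converted from MPA to EVR" where the Population section has "In total, 30 candidates will be enrolled and treated with conversion from MPA to EVR". With 25 against 50, uncorrected power is 14% and 31% for a doubling and a tripling. At the rejection rates cited in Background (30.2% against 19.4%), 30 against 60 gives about 22% power, so the conclusion does not hinge on the 5%.

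**The case against.** The strongest reply is that the plan never equates a non-significant test with safety. That is true. A reader might infer that a non-significant result would pass as safe, but no section says so, and the stated aim is to compare differences. What stands against the plan is narrower: it asks a safety question and supplies a difference test with no rule for reading it.

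The chi-squared test is also not the whole safety assessment. Kaplan-Meier estimates are planned for graft and patient survival, ANOVA for renal function, and serious adverse events, laboratory tests and an interim review of safety signals are included. This also stands, so the point is confined to rejection and infection; for graft loss and death the interval is an addition.

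A third reply is that an interval detects no more than the test. That is correct. The Newcombe lower limit exceeds zero in 14%, 35%, 58% and 77% of trials at true rates of 10%, 15%, 20% and 25%, against 15%, 36%, 60% and 78% for the uncorrected test. The limit is the sample size: at 80% power and 1:2 allocation, detecting 10% against 5% would need 312 everolimus patients, and 15% would need 99. The gain is in what is reported.

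Nor does the upper limit decide anything without a threshold. With both true rates at 5%, it is 10 points or more in 73% of trials. It should therefore be reported as a description of what cannot be excluded.

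**Conclusion.** The point holds as a matter of analysis choice and interpretation. For rejection, the planned test would miss a true doubling in about 85% to 93% of trials and a tripling in about 64% to 78%, depending on whether a continuity correction is used. Its non-significance cannot support a statement that the switch is safe or that rejection is similar. For infection the same logic applies, but the plan gives no rate from which to size it. The figures rest on 30 against 60 patients, a 5% control rate and two-sided 0.05.

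Two stronger readings are tempting and not supported. A reader might infer that any several-fold excess would usually be missed. With the uncorrected test that holds only up to about 3.6-fold; a fourfold excess is flagged about 60% of the time and a fivefold one about 78%. A reader might also infer that the plan errs in both directions, with false alarms as well as missed excesses. That depends on a choice the plan leaves open. At true rates of 2% to 5%, the chance of falsely flagging everolimus as worse is 3.4% to 4.1% without correction but 0.1% to 0.6% with Yates. The disagreement over 2/30 against 0/60 is a reason to specify the test, and no more than that.

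**What to change.** For rejection and infection, and for graft loss and death alongside the planned Kaplan-Meier estimates, make the difference in 12-month proportions with a two-sided 95% confidence interval (Newcombe or Miettinen-Nurminen) the main result. Replace chi-squared with an exact test (Fisher or Boschloo) as support. Name one interval and one test in advance, since borderline tables can differ between methods.

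Add two sentences: that p > 0.05 will not be taken as evidence of safety or similarity, and that the upper confidence limit will be reported as the largest excess the data cannot exclude.

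The control group must also be reconciled, because it defines what the difference estimates. The synopsis, Purpose and rationale and Treatment arms describe patients on, or converted to, azathioprine; Sample size calculation describes patients maintained on MMF or EC-MPS. The enrolment figures of 25 and 30 need reconciling as well.

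The cost is a few lines of analysis text and a more cautious safety statement. No extra patients are needed, and power does not increase.
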